### 11.3.2. Consent and Data Release Form Procedures and Documentation

Informed consent is a process that is initiated prior to an individual agreeing to participate in a study and continues throughout the individual's study participation. Discussion of risks and possible benefits of participation will be discussed with the patient and their families as requested prior to enrollment in the study and being considered a subject. The investigator, or designee, will explain the research study to the potential subject and answer any questions that may arise. All patients will receive verbal and written information in language at a level of complexity understandable to the patient about the purpose, procedures, and potential risks of the study and of their rights as research participants. Patients will have ample opportunity to review the informed consent form and to ask questions prior to providing their consent. The patients must be allowed additional time as desired to consider the study prior to agreeing to participate. Prior to participation in the study, the Patient Informed Consent Form will be signed and personally dated by the patient or his/her legal representative. Local regulations may allow for alternative approaches to the written informed consent form, such as witnessed phone consent. The site's alternative approach to obtaining informed consent must be approved by the sponsor and the site's EC/regulatory authority (if applicable) prior to implementation. Approval must be documented in the Investigator Site File.

The subject may withdraw consent at any time throughout the course of the study. The rights and welfare of the participants will be protected, and it will be emphasized to them that the quality of their medical care will not be adversely affected if they decline to participate in this study. The completed Patient Informed Consent Form must be collected from each enrolled subject and kept in the study subject files. Subjects will be notified in a timely manner of any significant new information that develops over the course of the study that may affect their willingness to participate.

The informed consent will include an authorization for use and disclosure of the subject's protected health information, in accordance with local regulations. Subject confidentiality will be maintained throughout the clinical study in a way that assures that individual subject data can be tracked back to the source data. For this purpose, a unique subject identification code will be used that allows identification of all data reported for each subject. Data relating to the study may be made available to third parties, provided the data are treated as confidential and that the subject's privacy is guaranteed.

As applicable per local regional requirements, a data release form may also be required and must be obtained prior to releasing patient information, if required. Similar to consenting procedures, the consent discussion must be conducted in non-technical wording understandable for the patient and the patient must have ample time and opportunity to inquire about further details. Once a patient decides to participate in the study, the written data release form must be signed and dated by both the investigator and the patient. The original, signed and dated data release form must be retained by the investigational site for monitoring, and a copy provided to the subject.

## 11.4. Participant and Data Confidentiality

During this clinical investigation, all representatives of the Sponsor will comply with all in-country privacy laws and regulations regarding contact with subjects, their medical record information, copying of information, and protection of the subject identities.

All information and data sent to Cerenovus concerning subjects or their participation in this clinical investigation will be considered confidential. Only authorized Cerenovus personnel or representatives (including contracted service providers, i.e. Imaging Core Lab, Central Clot Lab, Clinical Research Associate etc.), representatives of regulatory agencies will have access to these confidential files upon request (including, but not limited to, admissions/discharge summaries for hospital admission occurring during a subject's study participation and autopsy reports for deaths occurring during the clinical investigation). All data used in the analysis and reporting of this evaluation will exclude identifiable reference to the subject.

### 11.4.1. Research Use of Stored Human Samples, Specimens and data

Clot samples and related data collected under this protocol may be used to further study the etiology of AIS. Any remaining clot material will be retained and may be used in further scientific testing associated with the study. Access to stored samples and data will be limited to study related personnel, to include Cerenovus appointed vendors and not for other researchers or research groups. Samples will not be used as part of genetic research, and will be used for study related research. This material will not be used outside of the study. Samples and data will be stored using de-identified codes assigned to subjects. Results of the testing will remain the property of Cerenovus.

## 11.5. Future Use of Stored Specimens

With the subject's consent and as approved by local EC, de-identified biological samples will be stored at the Clot analysis lab for future analysis associated with the PERFECT study. These samples could be used for research into the causes of AIS and will be used until the Research and Development testing is complete or the sample is completely used. Samples not completely used will be stored for future use in stroke related research for approximately 15 years.

The samples will only be available for researchers working for or delegated by Cerenovus and not for other researchers or research groups. There will be no transfer of the biological samples to third parties not delegated by Cerenovus.

## 12. Quality Assurance and Quality Control

Quality Control (QC) procedures will be implemented beginning with the data entry system and ongoing QC checks will be run on the database. Any missing data or data anomalies will be communicated to the site(s) for clarification/resolution.

Following written (Standard Operating Procedures) SOPs, monitors will verify that the clinical study is conducted, and data are generated, documented, and reported in compliance with the protocol, ISO 14155, GCP, and the applicable regulatory requirements. If noncompliance is identified, Sponsor will implement measures to secure compliance.

The investigational site will provide direct access to all study related information, source data/documents, and reports for the purpose of monitoring and auditing by the Sponsor, and inspection by local and regulatory authorities.

## 13. Data Handling and Record Keeping

### 13.1. Data Collection and Management Responsibility

Data collection is the responsibility of the site clinical study staff under the supervision of the investigator. The investigator is responsible for ensuring the accuracy, completeness, and timeliness of the data entered. The Sponsor is responsible for all data management activities. These activities include the development of a database, utilizing validated database software, into which all study data will be entered by the clinical sites. The Sponsor will be responsible for ensuring the overall integrity of the database.

Data protection will abide by regulation (EU) 2016/679 of the European Parliament and of the Council of 27 April 2016 on the protection of natural persons with regard to the processing of personal data and on the free movement of such data. Data transfer outside the EU and to the US will be performed under adequate levels of protection and inspired by data transfer modalities at least as protective as the data protection laws within Europe.

#### 13.1.1. Electronic Case Report Forms

Electronic CRFs have been developed to capture the information outlined in this study protocol. Data on these eCRFs will be monitored, corrected if necessary, and entered into a validated database. All changes made to the data will be tracked in the electronic audit trail, recording the current value, previous value, reason for change, date timestamp of data entry/change, and the name of the person who changed the data. The investigator will electronically sign all subject eCRFs as verification that the data have been reviewed and correctly reflects source documentation. Data from these eCRFs will be used to provide analysis of this study.

### 13.1.2. Source Documentation

Data entered on to the eCRFs will be obtained from source documentation, such as hospital procedure reports, admission and discharge summaries, and other hospital or physician office/clinic documents. If no standard hospital or clinic document exists to capture information required specifically for this clinical investigation, a source worksheet may be developed to record this information. These source documents will serve as the basis for monitoring subject specific information against the eCRFs.

Electronic subject records will be considered source documents on the condition that the hospital's database is a validated system. If this is not the case, certified electronic record copies will have to be printed and added to the subject's paper file. A print-out of a completed eCRF cannot be used as source documentation.

### 13.1.3. Study Records

Regulations require that investigators maintain information in the subject's medical records, which corroborate data collected on the eCRFs. The Investigator is responsible for maintaining medical and study records for every subject participating in the clinical study (including information maintained electronically such as digital imaging). The Investigator will also maintain *original* source documents from which study-related data are derived, which include, but are not limited to:

- Clinic progress notes recording subject's medical history and medications
- Medical charts with operative reports and condition of subject upon discharge
- Medical records regarding device and procedure related Serious Adverse Events, including treatment and clinical outcome
- Results of diagnostic examinations
- Imaging (such as x-rays, MRIs), as well as the report of the radiologist's reading/interpretation of diagnostic imaging
- Shipping records and traceability for clots sent for histopathological analysis
- Notes of phone calls and/or correspondences indicating investigational site's attempts to follow study subjects at the required follow-up visits until subject's participation in the study is complete or terminated
- Records relating to subject death (e.g., death certificate, autopsy report)
- Print-outs of source data generated by technical equipment (e.g., x-rays, MRIs) must be filed with the subject's records.

Only authorized Cerenovus personnel or representatives, authorized site personnel, and local government authorities, will have access to these confidential files.

#### **13.1.4. Health Economic Data**

Subject hospitalization information will be collected in the eCRF by the investigator and study-site personnel for all subjects throughout the study. Subject admission and discharge date will be collected for the index procedure. Re-hospitalization data for unscheduled events will include admission and discharge date.

#### **13.1.5. Data Reporting**

The investigator, or designated individual, is responsible for timely completion of all data from the study via the eCRFs supplied by Cerenovus. The investigator/delegated individual is required to electronically sign the eCRF on the appropriate pages to verify that he/she has reviewed, and attests to the correctness, of the recorded data. Completed eCRFs will be reviewed and monitored at the investigational site by Cerenovus, personnel or designee at regular intervals throughout the study. The investigator and institution must permit inspection of the study files and subject eCRFs by such representatives and/or responsible government agencies.

Investigators are required to prepare and submit accurate and timely reports on this study to the EC and Cerenovus as applicable.

#### **13.1.6. Data Verification and Review**

Cerenovus will track the amount of missing data and contact sites as appropriate to instruct them on steps to minimize missing data and remain compliant with protocol required assessments. Missing or unclear data will be queried as necessary throughout the study. Cerenovus will request further documentation such as physician and/or radiology reports when complications or malfunctions are observed and reported. Cerenovus will be responsible for auditing the database and confirming the overall integrity of the data.

#### **13.1.7. Final Data Analysis**

All exported datasets for analyses will undergo a final data review before final database lock. Once all critical data are monitored and locked, the final analyses of clinical investigation data will be performed.

#### **13.1.8. Study Record Retention and Archiving**

The sponsor and principal investigator shall maintain the clinical investigation documents as required by the applicable regulatory requirement(s). It is the principal investigator responsibility to retain study essential documents and source documentation that support the data collected on the study subjects for at least two years after the final report. They shall take measures to prevent accidental or premature destruction of these documents. The principal investigator or sponsor may transfer custody of records to another person/party and document the transfer at the investigation site or at the sponsor's facility. These documents may be retained for a longer period if required by local laws and/or an agreement with Cerenovus. Prior to disposal of any records, the Investigator should notify

Cerenovus. The investigator will take measures to ensure that these essential documents are not accidentally damaged or destroyed. If for any reason the investigator withdraws responsibility for maintaining these essential documents, custody must be transferred to an individual who will assume responsibility. Cerenovus must receive written notification of this custodial change.

Each site must maintain a file of all documents and records relating to the conduct of this study that will include but will not be limited to the following documents:

- A copy of the Protocol and each Amendment (if applicable)
- EC Approval(s) for the Protocol, Protocol Amendment(s) and study ICF(s)
- EC approved ICF(s) template,
- EC and Sponsor Correspondence, including Reports
- Clinical Study Contract, fully executed
- Principal Investigator, Sub-investigator(s), site personal Curriculum Vitae
- Protocol Signature Page (s)
- Site Training Records
- Study Personnel Authorization Form (Site Delegation Log)
- Screening and Enrolment Log
- Subject Identification Log (not to be removed from site)
- IFU
- ICFs for each subject enrolled

Only authorized Cerenovus personnel or representatives, authorized site personnel, and local government authorities, will have access to these confidential files.

## 14. Protocol Deviations

The investigator is responsible for ensuring that the clinical investigation is conducted in accordance with the procedures described in the protocol, and any conditions required by the reviewing EC. A protocol deviation is a failure to comply (intentionally or unintentionally) with the requirements of the clinical study as specified in the protocol. Examples of protocol deviations include late visits, missed visits, required follow-up testing not completed, visit out of window, non-adherence to inclusion/exclusion criteria, etc. and shall be reported to the Sponsor through the eCRFs.

Any standard of care assessments performed outside of the protocol requirements prior to consent/enrollment will be considered an eligibility deviation. Deviations will be reviewed and assessed by the Sponsor.

It is the responsibility of the site to use vigilance to identify and report deviations to the Sponsor and EC per guidelines. The study monitors shall verify that the conduct of the study is in compliance with the approved protocol and applicable regulations and shall identify deviations and any issues of noncompliance. Corrective and preventative actions will be implemented promptly as necessary and significant protocol deviations that raise subject safety concerns or indicate repeat noncompliance may be grounds for investigator disqualification.

The investigator is not allowed to deviate from the protocol except under emergency circumstances to protect the rights, safety and well-being of study participants. Under emergency circumstances, deviations from the protocol to protect the rights, safety and well-being of human subjects may proceed without prior approval of the sponsor and the ethics committee. Such deviations shall be documented and reported to the sponsor and ethics committee as soon as possible.

## **15. Data and Publication Policy**

Publications and/or presentation of the clinical investigational results will be coordinated between Cerenovus and the clinical investigation author(s). Authorship will be determined prior to development of any manuscript. All information concerning the study device, Sponsor operations, patent application, manufacturing processes, and basic scientific data supplied by the Sponsor to the investigator and not previously published, are considered confidential and remain the sole property of the Sponsor.

## **16. Study Administration**

### **16.1. Study Registration**

This study will be registered on the clinical trial registries and results data banks including, but not limited to [www.ClinicalTrials.gov](http://www.ClinicalTrials.gov).

### **16.2. Steering Committee**

A Steering Committee of experts with experience in the areas of neurosurgery, neurology or interventional neuroradiology will be appointed for this study. The responsibilities of the Steering Committee include:

- Consultation on study design, protocol development, subject eligibility inquiries, data to be collected, analyses to be performed and provide oversight of the study
- Review of clinical data and statistical analyses, assist in data interpretation and writing
- Provide oversight of the study

## **17. Conflict of Interest**

The term “conflict of interest” refers to situations in which financial or other personal considerations may compromise or have the appearance of compromising a researcher's professional judgment in conducting or reporting research. Cerenovus will make every effort to safeguard against conflicts of interest to assure the integrity of the data, subject safety and investigator objectivity.

7.3	Demographic and Baseline Characteristics.....	7
7.4	Procedural Characteristics.....	7
7.5	Primary and Secondary Endpoints.....	7
7.5.1	Primary Endpoint.....	8
7.5.2	Secondary Endpoints	8
7.5.2.1	Secondary Effectiveness Endpoints.....	8
7.5.2.2	Secondary Safety Endpoints.....	9
7.6	Health Economic Endpoints.....	10
7.7	Clot Analysis	10
7.8	Analyses of Adverse Events (AEs).....	11
7.9	Plans for Interim Analyses	12
7.10	Handling of Missing Data	12
7.11	Sensitivity Analyses.....	12
7.12	Subgroup Analysis.....	12
7.13	Additional Analyses.....	13
7.14	Changes from Planned Analyses	13

1 Study Design

This is a prospective, multi-center, single-arm, post-market clinical follow-up study that will enroll approximately 100 subjects at approximately 10 sites primarily in Europe, with clot collection for follow-on histopathological analysis. Subjects will be included in the study for a period of 3 months after the procedure, including follow up visits at 24 hours, 7 days (or discharge) and 90 days after the procedure.

2 Treatment Assignment

This is a single arm study and all enrolled subjects are intended to be treated with the study device, the EMBOVAC Aspiration Catheter.

3 Interval Windows

Study reports will be summarized using analysis visits as defined below.

- 24 Hours post-procedure (-12 to +48 hours)
- 7-Day/Discharge (-1 to +7 days)
- 90-day follow-up (± 15 days)

The study schedule is to be adhered to as closely as possible for all subjects. Data will be summarized by scheduled visit. Measurements outside the analysis windows will be considered as missing in the analysis. In the case of repeated measurements taken at the same visit, the most recent measurement with non-missing values will be used unless specified otherwise.

4 Levels of Significance

No hypothesis tests are planned in the study. All confidence intervals will be reported at a two-sided 95% confidence level. These confidence intervals will not be used for statistical inferences, but for clinical reference purpose and are intended to convey precision in the estimates.

5 Analysis Sets

The following analysis sets are defined in the study:

- **Modified Intent-to-Treat (mITT) Analysis Set**

The mITT analysis set will consist of enrolled subjects who have received treatment (at least one pass; a pass being defined as use of aspiration followed by evaluation of revascularization with angiography) with the study device.

A subject is considered enrolled in this study once the physician confirms subject meets all eligibility criteria and the subject signs the informed consent.

The mITT analysis set will be used to analyze effectiveness endpoints.

- **Safety Analysis Set**

The safety analysis set will consist of all enrolled subjects in whom the treatment was attempted, defined by the advancement of the EMBOVAC Aspiration Catheter inside of the subject.

The safety analysis set will be used to analyze safety endpoints.

6 Sample Size Justification

There is no statistical power calculation and no hypothesis tests for this post-market study. 100 subjects are deemed sufficient to characterize the performance of EMBOVAC Aspiration Catheter.

Approximately 100 subjects will be enrolled. With an enrolled sample size of 100 and an attrition rate of no more than 5%, the precision (margin of error) for the primary endpoint is anticipated to be around 8.0% based on 2-sided 95% confidence intervals, where the primary endpoint rate is estimated to be 80%.

$$\text{Margin of error} \approx 1.96 \times SE = 1.96 \times \sqrt{\frac{p(1-p)}{n}} = 1.96 \times \sqrt{\frac{0.8 \times (1-0.8)}{95}} = 8.0\%$$

where SE denotes the standard error and p denotes the proportion of subjects who achieve the primary endpoint.

7 Analyses to be Conducted

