## SCHEDULE OF ASSESSMENTS

**Table 1 Schedule of Assessments**

Assessments	Enrollment				Follow-up	
	Baseline	Procedure	24hrs post-procedure (+/- 12 hrs)	7 days/ discharge (- 1/+7 days) (whichever comes first)	📞 90 Day Follow-up (+/- 14 days)	Unscheduled (6)
Eligibility Screening	X	X	X	X		
Informed Consent	Patient consent may be obtained up to 45 days post procedure					
Demographics and Medical History	X					
IV t-PA administration	O					
Imaging 	X		X			O
NIH Stroke Scale (NIHSS)	X 		X 	O	O	O
Modified Rankin Scale (mRS)	X 			O	X 	O
Angiography 		X				
Review of Reportable AEs 		X	X	X	X	X
Clot Collection 		X				
Health Economics Data Collection		X	X	X	X	X

(1) Imaging will be sent to independent Imaging Core Lab for review

(2) Procedural angiography will be sent to Imaging Core Lab for review

(3) Per pass clot collection to be sent to Clot Analysis Lab for processing

(4) If more than one NIHSS was performed during this time period, select the worst (highest) value

(5) To be administered pre-procedure by a qualified evaluator; pre-stroke mRS should reflect the subject's condition just prior to the stroke onset. For example, if the subject was hospitalized during stroke onset, the subject's reason for hospitalization should be taken into account when evaluating the subject's pre-stroke mRS

(6) Assessments should be completed for unscheduled visits from the time of Discharge up to (but not including) the 90-day Follow-up, where imaging, NIHSS or mRS is performed as part of stroke management care for the subject

(7) The 90 day mRS must be performed by a qualified independent evaluator. This may be performed by phone per the site's SOC.

(8) AEs will be reported and recorded (via eCRF) if any of the following apply: (a) The event is neurological in nature (b) The event is a serious adverse event (SAE) (c) AE where causality is related to the device or procedure.

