**Table 3 eTICI Scale**

0	No reperfusion; 0% filling of the downstream territory,
1	Thrombus reduction without any reperfusion of distal arteries
2	
 
• 2a Reperfusion in less than half (1-49%) of the territory
 
• 2b50 Reperfusion in (50-66%) of downstream territory
 
• 2b67 Reperfusion in (67-89%) of downstream territory
 
• 2c Reperfusion in (90-99%) of downstream territory
 

3	Complete or 100% reperfusion

All imaging should be in line with SOC. This includes CT or MR at baseline and 24 hours post procedure to assess any presence of hemorrhage, recanalization of the occluded artery, reperfusion, and infarct growth. Angiographic images obtained during the study should consist of (1) Baseline angiogram - prior to device advancement to assess clot location, (2) Post device angiogram - after each reperfusion attempt/pass of the device (a pass being defined as use of aspiration followed by evaluation of revascularization with angiography), (3) Final Angiogram – after all treatment has been completed. Any other imaging of the head or neck performed per SOC (for example as a result of clinical deterioration) must also be provided.

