7.1 General Conventions

Descriptive summary statistics will be presented for all endpoints. The number and percentage of subjects will be summarized for categorical variables. Unless specified otherwise, percentages will be based on subjects with non-missing values. Descriptive statistics for continuous variables will include the number of subjects, mean, standard deviation, median, first quartile (Q1), third quartile (Q3), minimum and maximum. All statistical analyses will be performed using SAS® Studio, Version 9.4 or later.

- **Baseline**

Unless specified otherwise, the last non-missing measurement collected during the baseline visit is considered as the baseline measurement (prior to the start of the index procedure).

- The pre-stroke mRS score will be considered as the baseline mRS score.
- The highest (worst) NIHSS score will be considered as the baseline NIHSS score should a subject have more than one non-missing NIHSS score at baseline.

- **Study Day**

Unless specified otherwise, study day will be calculated as the difference between the event/assessment date and index procedure date, i.e., event/assessment date - index procedure date, and the date of index procedure is considered as Day 0.

- Stroke onset date and time

Stroke onset date and time is defined as follows:

- For witnessed stroke, the stroke onset date and time as reported from the case report form (CRF) will be used;
- For un-witnessed stroke, the date and time when the subject was last seen well from CRF will be used.

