7.5.2 Secondary Endpoints

Secondary effectiveness endpoints will be analyzed in the mITT analysis set and secondary safety endpoints will be analyzed in the safety analysis set. Two-sided 95% CIs using binomial exact method will be constructed if required by the endpoint. Missing data will be excluded from the analysis unless instructed otherwise.

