7.5.2.2 Secondary Safety Endpoints

Device-related SAEs and all-cause mortality, Kaplan-Meier analysis (using product limit estimates) will be applied. Kaplan-Meier event rate and its associated two-sided 95% CIs using log-log transformation will be reported, the estimate of standard error will be computed using Greenwood's formula.

- **Devices related serious adverse events (SAEs) within 90 days of follow up as determined by an independent Clinical Events Committee**

Kaplan-Meier analysis will be performed to analyze the device related SAE rate within 90 days. Device related SAEs are considered as events; where the event date is the date of first event. Subjects without events will be censored at the date of last contact. The event rate at 90 days with associated 95% CIs will be provided. Device related SAEs beyond 90 days will be listed.

- **sICH at 24h post procedure specified according to the Heidelberg Bleeding Classification (HBC) as determined by an independent Clinical Events Committee**

sICH at 24 hours post procedure as specified by HBC will be assessed. The number and percentage of subjects with events will be summarized with CIs.

- **NIHSS at 24h post procedure**

The observed NIHSS total score at 24 hours post-procedure and changes from the baseline score will be summarized.

- **90 Day All-Cause Mortality**

Kaplan-Meier analysis will be performed to analyze all-cause mortality within 90 days. All-cause mortality is considered as the event; where the event date is the date of mortality. Subjects without events will be censored at the date of last contact. The event rate at 90 days with associated 95% CIs will be provided. Deaths beyond the 90 days will be listed.

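### Read literally, the SAP's 24-hour window and missing-data rules can drop an early sICH that has no in-window scan, and can admit first bleeds at 36 to 72 hours

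*SAP*

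**What the plan says.** SAP section 3 (Interval Windows) defines the first analysis visit as "24 Hours post-procedure (-12 to +48 hours"). It then states: "Measurements outside the analysis windows will be considered as missing in the analysis". For repeated values at one visit, "the most recent measurement with non-missing values will be used unless specified otherwise".

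Two later rules decide what happens to a missing value. SAP 7.1 says: "Unless specified otherwise, percentages will be based on subjects with non-missing values". SAP 7.5.2, for secondary endpoints, says: "Missing data will be excluded from the analysis unless instructed otherwise". SAP 7.10 plans no imputation that would reach sICH.

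The sICH paragraph in SAP 7.5.2.2 says "sICH at 24 hours post procedure as specified by HBC will be assessed" and asks for the number, percentage and confidence interval of subjects with events, as determined by the Clinical Events Committee (CEC). It gives no window of its own, no rule for an early scan and no rule for a death before the scheduled scan.

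Protocol 3.2.3 defines sICH as a new hemorrhage on brain imaging, timed at 24 hours after the intervention and adjudicated by the CEC. Protocol 6.1.1 requires that other head or neck imaging "performed per SOC (for example as a result of clinical deterioration) must also be provided". Protocol Table 1 sets the visit at "24hrs post-procedure (+/- 12 hrs"), and section 7.4 agrees.

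**The concern.** A symptomatic bleed in the first hours is likely to be imaged when the patient worsens, which may be before the window opens at 12 hours. If that patient then dies, or is not scanned again inside the window, the only scan showing the bleed is out of window. Under the default rules the value becomes missing and the subject is excluded. The subjects exposed to this are among the most severe cases, and they would leave the denominator as well as the numerator.

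At the other end, the SAP keeps the window open 36 hours longer than the protocol does. A first bleed in that interval would be reported as a 24-hour event.

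At stake is whether the sICH rate has a single definition. Two programmers could derive different rates from the same data, and interim results are intended for regulatory submissions (SAP 7.9).

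**Working it through.** **Windows**

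- SAP section 3: 24 − 12 = 12 h to 24 + 48 = 72 h.
- Protocol Table 1 and section 7.4: 24 − 12 = 12 h to 24 + 12 = 36 h.
- The lower limits agree. The upper limits differ by 72 − 36 = 36 h. SAP 7.14 lists only the 90-day mRS window as a change.

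**What the rules do to each kind of subject, read literally**

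| Subject | In-window scan? | Result |
|---|---|---|
| sICH imaged before 12 h, survives and is rescanned at 12–72 h | Yes | Not missing; the CEC can adjudicate |
| sICH imaged before 12 h, dies after 12 h with a scan between 12 h and death | Yes | Not missing |
| sICH imaged before 12 h, dies or is not rescanned, no scan at 12–72 h | No | Missing; out of numerator and denominator |
| First bleed imaged at 36–72 h | Yes by the SAP, no by the protocol | Counted as 24-hour sICH |

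**How other endpoints are treated**

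The SAP writes explicit rules elsewhere. Death is scored as mRS 6 (7.5.2.1). Device-related SAEs and mortality are analysed by Kaplan-Meier on event dates (7.5.2.2). Section 7.14 separates event dates from visit compliance, but only for the 90-day endpoints. Nothing comparable is written for sICH.

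**Size**

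The documents state no sICH rate and no precision for it. The only computed figure is the 8.0% margin for the primary endpoint. It reproduces, 1.96 × √(0.8 × 0.2/95) = 8.04%, but has no bearing here. What follows is therefore an illustration with assumed event counts.

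Let N be the safety set, e the true sICH and k the sICH cases set to missing. The full rate is e/N and the reported rate is (e − k)/(N − k). The fall is k(N − e)/[N(N − k)]. For N = 100, e = 5, k = 1 this is 95/9,900 = 0.96 percentage points.

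With N = 100 and e = 5, using the exact intervals named in SAP 7.5.2:

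| k | Reported | Exact 95% CI |
|---|---|---|
| 0 | 5/100 = 5.0% | 1.6–11.3 |
| 1 | 4/99 = 4.0% | 1.1–10.0 |
| 2 | 3/98 = 3.1% | 0.6–8.7 |
| 3 | 2/97 = 2.1% | 0.3–7.3 |

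Other assumed counts, for k = 0, 1, 2, 3:

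- e = 3, N = 100: 3.0%, 2.0%, 1.0%, 0.0%.
- e = 8, N = 100: 8.0%, 7.1%, 6.1%, 5.2%.
- e = 5, N = 95 (the SAP's 5% attrition): 5.3%, 4.3%, 3.2%, 2.2%.

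Each dropped case costs about 1 point throughout.

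Late bleeds work the other way. With N = 100, e = 5 and one case dropped, adding one first bleed at 36–72 h gives (5 − 1 + 1)/99 = 5/99 = 5.1%, against 5.0% if neither rule had acted. The two effects can cancel.

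**The case against.** A reader might infer that the SAP certainly discards every sICH found on an early deterioration scan and so biases the rate downward. The documents do not support that, for these reasons.

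- **sICH may not fall under the window rule.** Section 3 speaks of measurements summarized by visit, and its repeat-value rule suits NIHSS or mRS. The sICH paragraph speaks of CEC-determined events. A positive adjudication is not obviously a missing value, so the SAP can also be read as counting it whenever it occurred.
- **The definition leans towards event timing.** Protocol 3.2.3 compares NIHSS at diagnosis with the status just before worsening, and deterioration scans must be supplied. Adjudication detail is left to the CEC charter, which is not among the documents and may settle the matter.
- **Few subjects are exposed.** A 24-hour scan is scheduled for everyone, so a rescanned survivor is not missing.
- **Some may never be enrolled.** Exclusion criterion 1 names 24-hour imaging outside the protocol window, and no SAP rule can recover a patient who was screened out. Protocol 11.3.1 does foresee representative consent after an early death, so such subjects can still be in the safety set.
- **Nothing disappears from the study.** These bleeds would be in the adverse event tables (SAP 7.8) and deaths in the mortality analysis. The SAP also says its intervals are not for inference.

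All of this stands as a limit on the claim. It does not remove the gap: neither document says whether an sICH before 12 hours counts, or how a subject without an in-window scan is handled, and the written defaults point to exclusion. The 36 versus 72 hour discrepancy needs no interpretation.

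**Conclusion.** The point holds as an ambiguity with a literal reading that can drop cases. On that reading, an sICH imaged only before 12 hours in a subject with no in-window scan leaves the rate altogether, and a first bleed at 36 to 72 hours enters it against the protocol window.

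Each dropped case lowers the rate by about 1 percentage point at N of about 100. The number of such cases is unknown: losing 1 to 3 of 5 is an assumption with no support in the documents. Late bleeds raise the rate, so no net bias is established in either direction. The effect is confined to the sICH rate, one of four descriptive secondary safety endpoints. It is still worth closing before database lock, because the exposed cases are among the most severe and the remedy uses imaging that the protocol already requires.

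**What to change.** In SAP 7.5.2.2:

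- State that the section 3 windows and the missing-data exclusion do not apply to sICH.
- Count any CEC-adjudicated sICH from the start of the procedure to the end of the 24-hour window, on whichever scan showed it.
- Use the full safety analysis set as denominator. An unscanned subject without an adjudicated event then counts as event-free, so report how many subjects lack an in-window scan, including early deaths, with their CEC classification.
- Reconcile the SAP's 72-hour upper limit with the protocol's 36 hours, record the outcome in SAP 7.14 if the SAP departs from the protocol, and list later sICH separately.
- Check that the CEC charter uses the same start, end and handling of early deaths.

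The cost is one SAP paragraph and no new data collection for enrolled subjects. The downside is that the reported rate may be slightly higher.
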